### 6.1.10. Study Drug Exposure

Duration of study drug exposure in days during the acute and extension periods will be summarized by treatment and overall for all ITT patients in Study Period II and for all ITT patients entering Study Period III.

Total patient-years of exposure will also be displayed by treatment group and overall.

Duration of study drug exposure will be defined as the difference between the date of last dose of study drug in the respective study period and the date of first dose of study drug in the respective study period.

The first dose date of study drug for Study Period II is the first dose date collected on the eCRF. The first dose date for Study Period III will be one day after the visit 8 date.

The date collected on the eCRF module “date of last dose” is the last dose date of study drug for the whole study period. If the “date of last dose” collected in the eCRF is missing, then the last dose date will be imputed as the minimum of two dates: 1) the date determined by the number of days dispensed dose allowed; 2) the last non-missing disposition date.

The last dose date of study drug for Study Period II will be determined as following:

- For patients who did not enter the Study Period III or taper phase, the last dose date is the date collected in the eCRF module “date of last dose”;
- For all other patients, the last dose date will be imputed as the minimum of two dates during SP II as described above.

The last dose date of study drug for Study Period III will be determined as following:

- For patients who did not enter the taper phase, the last dose date is the date collected in the eCRF module “date of last dose”;
- For all other patients, the last dose date will be imputed as the minimum of two dates during SP III as described above.

Comparisons between treatment groups for duration of study drug exposure will be performed for Study Period II using an ANOVA with treatment and pooled investigative site in the model. Patient exposure durations will also be summarized categorically and assessed for treatment differences using Fisher’s exact test for Study Period II.

Number and percentages of patients with doses of DLX30 and DLX60 will be tabulated at each visit for all patients randomized to duloxetine during Study Period II and all ITT patients entering Study Period III.

Number and percentages of patients with modal dose of DLX30 and DLX60 will be summarized for all patients randomized to duloxetine during Study Period II and all ITT patients entering

Study Period III. The last prescribed dose at LOCF endpoint for Study Period II and III will be also summarized using this method.

The modal dose is defined as the dose that a patient was prescribed for the most number of days during the study period. If there is a tie in the greatest number of days on a dose for a patient, the modal dose will be set to the highest dose in the tie.

The mean daily dose is calculated as the mean of all doses that a patient was prescribed during the study period. The mean of all doses is calculated as sum of dose multiplied by the number of days on that dose divided by total number of days during the study period. The mean daily dose will be summarized for all patients randomized to duloxetine at Study Period II and all ITT patients entering Study Period III.

Dose adjustment by visit will be summarized as well.

Dose reduction due to adverse events will be listed.

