### 5.1. Summary of Study Design

Study F1J-MC-HMGW (HMGW) is a Phase 3b, multicenter, randomized clinical trial of duloxetine versus placebo for the treatment of JPFS in adolescents. The study design includes 4 study periods. Following Study Period I (screening phase), eligible patients enter Study Period II, the acute 13-week parallel, randomized, double-blind, placebo-controlled treatment period of duloxetine 30/60 mg QD. Upon completion of the 13-week double-blind period, patients enter Study Period III, a 26-week, open-label extension phase of duloxetine 30/60 mg QD. A 1-week drug taper period (Study Period IV) is required for all patients who discontinue for any reason between Visit 4 to Visit 8 during Study Period II, or who complete/discontinue Study Period III on duloxetine 60 mg QD.

Figure HMGW.5.1 illustrates the study design.

Abbreviations: DB = double-blind; DLX = duloxetine; OL = open-label; QD = once-daily

a After Visit 3, patients increased to 60 mg duloxetine can have their dose decreased 1 time, at a scheduled or unscheduled Visit. Once 60 mg dose is decreased to 30 mg, it cannot be increased again during Study Period II.

b At Visits 4 through 8, patients randomized to placebo or DLX 30 mg who discontinue prior to entering the open-label extension treatment period (Study Period III) will receive placebo in the drug taper period.

c At Visits 9 through 14 in Study Period III, dose increases are permitted at scheduled visits (to a maximum dose of 60 mg QD) and dose decreases are permitted at scheduled or unscheduled visits (to a minimum dose of 30 mg QD).

d Patients who complete/discontinue Study Period III on DLX 30 mg do not need to enter the drug taper period.

**Figure HMGW.5.1** Illustration of study design for Protocol F1J-MC-HMGW.

Study Period I is a screening period of approximately 1 week in duration, but not more than 30 days, during which patients will be screened for study eligibility.

Study Period II is a 13-week, acute treatment period. During Study Period II, at Visit 2, patients who meet all study criteria for enrollment will be randomly assigned in a 1:1 ratio to duloxetine or placebo by a computer-generated random sequence using an interactive voice response system (IVRS). All patients will receive investigational product (IP) beginning at Visit 2 and will be instructed to start taking their IP the morning after Visit 2.

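### SAP Section 6.1.10 defines exposure in days as last dose date minus first dose date, which drops one day per dosed patient in each study period

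*SAP*

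**What the plan says.** Section 6.1.10 sets the unit: "Duration of study drug exposure in days during the acute and extension periods will be summarized by treatment and overall". The rule for duration is "defined as the difference between the date of last dose of study drug in the respective study period"; what is subtracted is the first dose date of that same period. Neither this section nor any other adds a day. The same section states: "Total patient-years of exposure will also be displayed by treatment group and overall".

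Three other statements fix the dates that enter the rule:

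- **Start of Study Period II.** The first dose date comes from the eCRF. Under Section 5.1, patients "will be instructed to start taking their IP the morning after Visit 2".
- **Start of Study Period III.** "The first dose date for Study Period III will be one day after the visit 8 date". The Visit 8 day therefore belongs to Study Period II.
- **End of each period.** The recorded eCRF date is used for patients who do not go on to a further period. If that date is missing, "then the last dose date will be imputed as the minimum of two dates": one set by the supply dispensed, the other by disposition. The same imputation applies in Study Period II to everyone who enters Study Period III or taper, and in Study Period III to everyone who enters taper.

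**The concern.** Dosing is once daily. The days covered from first to last dose are an inclusive count of dates, that is, the date difference plus 1. A plain difference counts the gaps between doses, and there is one fewer of these than there are dosing days.

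Because the rule is applied to each period separately, a patient treated in both periods loses two days. What is at stake is the accuracy of the reported durations, of the total patient-years, and of the counts in the categorical exposure summary if its cut-points fall where one day matters.

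**Working it through.** The SAP states no exposure or patient-year figure, so there is nothing to reproduce. The check is date arithmetic on the stated rule.

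**Inputs from the SAP**

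- Study Period II lasts 13 weeks = 91 days, and Study Period III lasts 26 weeks = 182 days (Section 5.1).
- Planned sample size is 184, with about 81% completing Study Period II (Section 5.2). 0.81 × 184 ≈ 149 patients.
- First and last dose rules are those of Section 6.1.10.

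**Assumptions, not in the SAP**

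- A patient-year is 365.25 days.
- All 184 patients are dosed.
- An on-time completer's last dose date is the closing visit of the period (Visit 8 or Visit 15).
- Study Period II dropouts average between 7 and 84 days on drug.
- All 149 Study Period II completers enter and complete Study Period III.

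**One patient on schedule, with Visit 2 as day 0**

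| | First dose | Last dose | SAP rule (last − first) | Inclusive (+ 1) |
|---|---|---|---|---|
| Single dose | day 1 | day 1 | 0 | 1 |
| Study Period II completer | day 1 | day 91 (Visit 8) | 90 | 91 |
| Study Period III completer | day 92 | day 273 (Visit 15) | 181 | 182 |

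Under the SAP rule the two completed periods sum to 90 + 181 = 271 days. One plain difference over the whole span gives 273 − 1 = 272, and the inclusive count is 273. The separate periods therefore do not add up even for a reader who accepts plain differences. With the extra day they do: 91 + 182 = 273.

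**Relative shortfall for one patient = 1 / inclusive days**

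| Inclusive days | 1 | 7 | 14 | 28 | 91 | 182 |
|---|---|---|---|---|---|---|
| Shortfall | 100% | 14.3% | 7.1% | 3.6% | 1.1% | 0.55% |

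**Study Period II patient-years**

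- Loss: 184 × 1 / 365.25 = 0.504.
- Inclusive total, dropouts averaging 7 days: 184 × (0.81 × 91 + 0.19 × 7) / 365.25 = 184 × 75.04 / 365.25 = 37.8. Loss 0.504 / 37.8 = 1.3%.
- Inclusive total, dropouts averaging 84 days: 184 × (0.81 × 91 + 0.19 × 84) / 365.25 = 184 × 89.67 / 365.25 = 45.2. Loss 0.504 / 45.2 = 1.1%.

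The percentage barely depends on the assumed dropout time.

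**Study Period III patient-years, 149 completers**

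- SAP rule: 149 × 181 / 365.25 = 73.84.
- Inclusive: 149 × 182 / 365.25 = 74.25.
- Loss: 0.41 patient-years, or 0.55%.

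**What the shift reaches.** Adding 1 to every duration moves both arm means by the same amount and leaves the residuals as they were. The Study Period II ANOVA treatment difference and its p-value are therefore unchanged. Fisher's exact test on categorical duration could change only for patients within one day of a cut-point, and the SAP gives no cut-points.

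**The case against.** The strongest objection is that elapsed time and inclusive days are two conventions, that they differ by about 1% over these periods, and that nothing inferential rests on the choice. Section 6.1.14.1 reports adverse events as numbers and percentages of patients and as Kaplan-Meier times. No safety rate in the SAP is divided by patient-years. All of this stands, and it sets the size of the point. It does not rescue the rule, because the quantity is labelled exposure in days and the periods, as defined, do not add up.

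It is also fair to say that an inclusive count is not the number of doses taken. Section 6.1.11 counts 80% to 120% of prescribed capsules as compliant, so missed doses remain inside either count. The extra day corrects the span between two dates and nothing more.

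Three stronger readings are tempting, and the SAP does not support them:

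- **Exposure is understated for every patient.** Randomized patients who were never dosed lose nothing. For the many patients whose last dose date is imputed, the imputed date may fall before or after the true last dose, so error against actual dosing can add to the missing day or offset it. The shortfall is certain only relative to the dates used.
- **Early tolerability is misjudged.** The relative error is largest for very early dropouts, but tolerability is assessed through adverse events, discontinuations and time to discontinuation, none of which uses this duration.
- **Mean daily dose is distorted.** Section 6.1.10 divides dose-days by the total days in the study period, but does not say that this denominator is the exposure duration.

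**Conclusion.** The definition is wrong as written, and the consequence is small. Relative to the recorded or imputed dose dates, each dosed patient loses one day per study period. The size is about 0.50 patient-years in Study Period II (1.1% to 1.3% of the total, under the stated completion rate and an assumed dropout mean of 7 to 84 days) and 0.55% for Study Period III completers. The patient-year figures also assume that all 184 patients are dosed and that a year is 365.25 days.

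The error reaches only the descriptive exposure and patient-year displays and, possibly, patients on a cut-point of the categorical summary. The point is worth making because a stated formula yields a wrong reported number and is free to correct. It casts no doubt on the efficacy or safety conclusions.

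**What to change.** In Section 6.1.10, define duration of exposure as (last dose date − first dose date) + 1, separately for Study Period II and Study Period III, and obtain total patient-years by summing these durations. State the divisor that converts days to years.

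The cost is one sentence in the SAP and one line of code. No data collection, sample size or inferential analysis is affected.

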### **6.1.11. Treatment Compliance**

The percentage of patients deemed compliant will be summarized by visit and overall for Study Period II, and for all patients entering Study Period III. A patient will be considered to be compliant with study drug for each interval if they take between 80% and 120% of study drug capsules prescribed for that interval. Overall compliance is defined as having been compliant at all nonmissing visits within each study period. Comparisons between treatment groups will be performed for Study Period II both overall and at each visit using Fisher's exact test. Descriptive statistics will be used to present the two treatment groups for the Study Period III results and will include only those patients who entered the study period.

A listing of study drug compliance will be presented for all study periods.

### **6.1.12. Previous and Concomitant Therapy**

Previous therapies for fibromyalgia are those therapies for the treatment of fibromyalgia that started and stopped prior to or at baseline (Visit 2). Concomitant therapies include psychotherapy, physical therapy, and concomitant medication. Concomitant therapies for Study Period II are those which started prior to visit 2 or after visit 2 and are taken during SP II. Concomitant therapies for Study Period III are those that started prior to visit 8 or after visit 8 and are taken during SP III.

Previous therapies for fibromyalgia will be summarized by treatment group for all ITT patients, displaying the number and percentage of patients by preferred term for Study Period II and for all ITT patients entering Study Period III. Concomitant medications will be summarized in the same way for Study Period II and Study Period III, respectively. The tables will be sorted in decreasing frequency of preferred terms. The denominator used for calculating the percentages will be the total number of patients included in the ITT population for each treatment group for Study Period II, and will be the total number of patients included in the ITT patients entering Study Period III for each treatment group for Study Period III. Concomitant psychotherapy and

concomitant physical therapy will also be summarized by treatment group for Study Period II and Study Period III separately. Comparison between treatment groups will be performed using Fisher's exact test for Study Period II.

A listing of concomitant therapy will be presented for SP II and SP III.

### 6.1.13. Efficacy Analyses

#### 6.1.13.1. Primary Outcome and Methodology

The primary objective of this study is to evaluate the efficacy of duloxetine 30/60 mg once daily compared with placebo on the reduction of average pain severity as measured by the BPI average pain severity rating during the Study Period II in adolescents with JPPFS.

The primary efficacy analysis will be the contrast between duloxetine and placebo at the last visit in Study Period II (Visit 8, Week 13) from a MMRM analysis on change from baseline in the BPI average pain score as described in Sections 6.1.2 and 6.1.3.

#### 6.1.13.2. Additional Secondary Analyses

Table HMGW.6.3 presents the secondary efficacy measures and derived variables that will be evaluated for Study Period II. Baseline and endpoint definitions are described above in Table HMGW.6.1.

Maintenance of effect of duloxetine 30/60 mg QD during Study Period III will be assessed using the BPI average pain severity in only the duloxetine treated acute phase responders (defined as those patients with  $\geq 30\%$  pain reduction from baseline on the BPI average pain severity measure at the last non-missing assessment in Study Period II). The T-statistics will be used to evaluate the maintenance of effect of duloxetine 30/60 mg QD during Study Period III. If the upper bound of the one-sided 97.5% CI of the change from baseline to endpoint for patients in the extension treatment phase who responded to duloxetine 30/60 mg QD in Study Period II (acute phase duloxetine responders) is less than or equal to the pre-specified margin of 1.5, then the treatment effect of duloxetine was maintained during the extension treatment phase. The margin of 1.5 points on the BPI average pain scale was extrapolated from data and results of prior adult duloxetine clinical studies, where a mean pain reduction of 3 to 4 points were observed for patients who met pre-defined response criteria after 2-3 months duloxetine therapy. Therefore, an increase of 1.5 indicates that the average pain at end of extension phase would still be 1.5 to 2 points below the pain severity prior to initiating acute treatment, which would be considered as clinical meaningful.

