Patients randomly assigned to placebo will remain on placebo throughout Study Period II.

Patients randomly assigned to the duloxetine treatment group will remain on duloxetine throughout Study Period II. Duloxetine patients will initially take a 30 mg QD dose of duloxetine for 1 week. Starting at Visit 3 through Visit 6, the dose can be increased from 30 mg QD to 60 mg QD. By Visit 4, comorbid MDD and/or GAD patients receiving a 30-mg QD dose should be increased to a 60-mg QD dose, unless the patient is experiencing significant intolerance to the 30-mg dose. Beginning at Visit 7, no dose increases can be made. Dose-escalation criteria for all patients is based on investigator's clinical judgment. Dose increase can only occur at scheduled study visits. If necessary due to intolerability, for those patients on a 60-mg QD dose, a one-time dose decrease to 30 mg may occur at a scheduled or unscheduled visit. Once the 60-mg dose is decreased to 30 mg, it cannot be increased again during Study Period II. If the patient has already had their 1 dose decrease, and at a subsequent time cannot tolerate the investigational product dose well enough to remain compliant, the patient should be discontinued.

Study Period III is a 26-week, open-label extension treatment phase. Patients randomized either to the duloxetine or placebo treatment group during Study Period II will enter Study Period III on a 30-mg dose of duloxetine for 1 week. The duloxetine dose may be increased to 60 mg QD only at a scheduled Visit starting at Visit 9 (Week 14). As in Study Period II, additional dose-escalation consideration should be given to all patients with comorbid MDD and/or GAD at study entry. At Visit 9, the comorbid MDD and/or GAD patients should have their 30-mg dose increased to 60 mg, unless the patient is experiencing significant intolerance to the 30-mg dose. From Visit 9 to Visit 14, dose modifications are allowed. Dose increases (up to 60 mg QD) are only permitted at scheduled visits. Dose decreases (down to 30 mg QD) are permitted at either scheduled or unscheduled visits. Dose adjustments are to be based on the investigator's clinical judgment of treatment response and tolerability at the patient's current dose.

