### 6.1.13.3. Sensitivity Analysis

To assess the possible impact of missing data on the primary efficacy analysis conclusions, a sensitivity analysis will be performed leveraging a delta based approach. The approach for this analysis is to vary the assumptions of missing data for the primary analysis in a systematic way. Basically, the method will be to predict the missing outcomes and then add a value ( $\Delta$ ) to the predictions in the duloxetine treatment group consistent with the sensitivity approach suggested in Permutt (2015). This procedure will be repeated multiple times for different values of  $\Delta$  using the following steps:

- 1) Predict the missing outcomes for each treatment via multiple imputation based on observed primary endpoint and baseline values. Such imputation will be carried out using a Markov Chain Monte Carlo method with a Jeffreys prior via SAS® PROC MI. Thirty (30) such imputations will be created.
- 2) Add the corresponding  $\Delta$  value to the imputed duloxetine treatment values.
- 3) Conduct the primary analysis separately for each of the 30 imputations.
- 4) Combine the results of these analyses using Rubin's combining rules, as implemented in SAS® PROC MI ANALYZE.

The above steps will be repeated multiple times for different values of  $\Delta$  with  $\Delta$  ranging from (0, twice the observed treatment effect seen in the primary analysis). For example, if the overall mean change from baseline for placebo is -3.6 and the maximum overall treatment difference is -1.5, then  $\Delta$  would range from (0,7.2).

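### The maintenance rule in SAP 6.1.13.2 concludes that a duloxetine treatment effect was maintained, from an uncontrolled single-group bound not tied to the primary result; a drug with no effect can meet it

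*SAP*

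**What the plan says.** SAP Section 6.1.13.2 says that maintenance "will be assessed using the BPI average pain severity in only the duloxetine treated acute phase responders", meaning those with at least a 30% reduction at the last non-missing assessment of Study Period II. The test is on one group: "If the upper bound of the one-sided 97.5% CI of the change from baseline to endpoint" in the extension "is less than or equal to the pre-specified margin of 1.5, then the treatment effect of duloxetine was maintained during the extension treatment phase". Under Table HMGW.6.1 the extension baseline for efficacy is the last of Visits 3-8.

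The margin is justified from adult studies, "where a mean pain reduction of 3 to 4 points were observed for patients who met pre-defined response criteria". The SAP infers that after a rise of 1.5 the "average pain at end of extension phase would still be 1.5 to 2 points below the pain severity prior to initiating acute treatment".

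On the design, Section 5.1 says: "Study Period III is a 26-week, open-label extension treatment phase". It adds that "Patients randomized either to the duloxetine or placebo treatment group during Study Period II will enter Study Period III", and both groups then take duloxetine. Section 6.1.2 plans no test of PLA/DLX against DLX/DLX in that period. Sections 6.1.2 and 6.1.6 use no multiplicity adjustment, and no hierarchy links the maintenance conclusion to the Week 13 contrast.

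**The concern.** The quantity tested is a mean change within a group selected for having improved. The conclusion attached to it concerns a treatment effect of duloxetine. With no untreated or placebo group in the extension, improvement caused by the drug and improvement that would have occurred and persisted anyway look the same to this rule. The rule also runs whatever the primary analysis shows. Applied literally after a Week 13 contrast that shows no difference from placebo, it could still report that an effect was maintained when none had been demonstrated. The rule serves a stated secondary objective (Section 4.2) and its verbal conclusion is fixed in advance, so the wording would pass into the report.

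**Working it through.** **1. The plan's own figure.** Taking the margin from the adult responder reductions gives 3 - 1.5 = 1.5 and 4 - 1.5 = 2.5. The SAP prints 1.5 to 2, so only the lower end reproduces. Halving the reduction (3/2 = 1.5, 4/2 = 2.0) gives the printed range, but that is not a fixed 1.5-point margin. This is a side point. What matters here is that the margin rests on within-group reductions and not on a difference from placebo. Section 5.2 sizes the trial for a duloxetine-placebo difference of 1.0 point, so the permitted rise exceeds the whole planned mean difference. Responders may have a larger drug effect than average, but nothing in the SAP isolates it.

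**2. What passes.** The rule is: mean rise + t(0.975, n-1) x SD/√n ≤ 1.5. With 30 responders and an SD of change of 2.0 (both assumed), the second term is 2.045 x 2.0/√30 = 0.75. An observed mean rise of up to 1.5 - 0.75 = 0.75 therefore passes.

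**3. Behaviour with an inert drug.** From the SAP (Section 5.2): 184 patients at 1:1 gives 92 per arm, and 92 x 0.81 = 74.5, or about 75 completers. From Table HMGW.6.2: entry BPI average pain of at least 4. Assumed, because the SAP gives no values: baseline mean 6, SD 1.3; mean acute change of -1.0 to -2.0 in both arms; SD of change 2.0 to 2.4; correlation ρ between the change to Visit 8 and the change to the extension endpoint; no drug effect and no further drift. Share of 2,000 simulated trials that meet the rule:

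| Mean change, SD | ρ = 0.5 | 0.6 | 0.7 | 0.8 |
|---|---|---|---|---|
| -1.0, 2.0 | 0.21 | 0.45 | 0.77 | 0.97 |
| -1.0, 2.4 | 0.10 | 0.26 | 0.60 | 0.92 |
| -1.5, 2.0 | 0.45 | 0.71 | 0.92 | 1.00 |
| -1.5, 2.4 | 0.25 | 0.50 | 0.80 | 0.98 |
| -2.0, 2.0 | 0.72 | 0.90 | 0.99 | 1.00 |
| -2.0, 2.4 | 0.45 | 0.69 | 0.93 | 1.00 |

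At ρ = 0.9 the share is about 1.00 throughout. Repeating the simulation moved the ends of these ranges by a few points (up to 0.75 at ρ = 0.5, down to 0.58 at ρ = 0.7), so the ranges are approximate. About 25 to 40 patients qualify as responders. Their mean acute reduction is 3.1 to 3.7 points, inside the SAP's 3 to 4 points although the drug does nothing.

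**4. Direction of regression to the mean.** Responders are chosen for low pain at the end of Study Period II, so their pain then tends to rise, by roughly (1 - ρ) x (responder reduction - mean reduction). For the first row at ρ = 0.5 this is 0.5 x (3.11 - 1.0) = 1.06; the simulated value is 1.08. Across the grid the mean rise is 0.2 to 1.2, always below 1.5. If non-specific improvement continues by a further 0.5 point in the extension (mean change -1.5, SD 2.2), the pass share is 0.80 to 1.00 for ρ from 0.5 to 0.8.

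**5. Futility.** Section 6.2 recommends termination if conditional power is below 0.6. Under the current-trend formula, continuing needs Z(t) ≥ √t x [1.96 + 0.253 x √(1-t)].
- t = 0.71 (the SAP's stated fraction): 0.843 x (1.96 + 0.253 x 0.539) = 1.77, which a null trial exceeds with probability 0.039.
- t = 150/184 = 0.815: 0.903 x (1.96 + 0.253 x 0.430) = 1.87, probability 0.031.

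So about 96-97% of null trials would receive a termination decision.

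**The case against.** The strongest reply is that Section 6.1.13.2 discloses what it measures. It describes a within-group change in responders, sets the margin against pain before treatment, and claims no superiority to placebo in the extension. Section 4.2 uses similar language for the open-label phase, and an uncontrolled extension is simply this trial's design. The lack of a hierarchy applies to all secondary analyses, not only this one. All of that stands, but none of it makes the fixed conclusion follow from the data.

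The futility rule also narrows the exposure considerably, since few null trials would pass the interim look. It is still not a gate. After a futility stop, Section 6.2 says only that the missing-data sensitivity analyses may be dropped, and a trial that continues can still miss its primary endpoint.

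Some stronger readings are tempting and do not hold:
- A reader might infer that regression to the mean helps the rule as much as placebo response does. After selection of responders it raises extension pain and works against the rule.
- A reader might infer that an inert drug would almost always pass. At a correlation of 0.5 the share can be as low as about 10%, and the SAP gives no figure that settles the correlation.
- A reader might argue that the SAP reserves the term treatment effect for the duloxetine-placebo contrast. Section 6.1.13.3 sets the range of delta by "twice the observed treatment effect seen in the primary analysis", but its worked example ends at 7.2. That is 2 x 3.6 (the placebo change), not 2 x 1.5 = 3.0 (the difference). Usage is not consistent enough to carry the point.
- A reader might look to placebo-arm responders in the extension to show non-specific persistence. They start duloxetine in Study Period III, so they cannot.

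**Conclusion.** The point holds. The conclusion fixed in Section 6.1.13.2 goes beyond what a single-group bound in an uncontrolled open-label period can show, and nothing makes it depend on the Week 13 contrast. With zero drug effect the rule is met in about 10-75% of trials at a correlation of 0.5, 60-99% at 0.7 and 92-100% at 0.8. These ranges rest on assumed baseline, placebo-type change, SD and correlation, and they describe trials that run to the end of the extension, before the futility rule is taken into account. The lack of control and of any link to the primary result does not depend on those assumptions. What the rule can support is narrower: on average, pain in acute-phase responders did not rise by more than 1.5 points while they took open-label duloxetine. The primary analysis and its estimate are unaffected.

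**What to change.** In Section 6.1.13.2:

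1. Replace the conclusion with: *mean pain improvement was maintained (rise not exceeding 1.5 points) in acute-phase responders who continued open-label duloxetine*. State alongside it that Study Period III has no concurrent control.
2. Add that the result will not be described as support for a maintained duloxetine effect unless the primary Week 13 contrast is statistically significant in favour of duloxetine. Even then, state that the extension was uncontrolled, because a significant primary result does not supply the missing comparison.

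Do not add a PLA/DLX responder row as evidence of non-specific persistence.

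The cost is a few sentences of SAP text. No data collection, design or estimate changes. The downside is a weaker claim for the sponsor.
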